Post-Intervention Survey 2: Once a participant has completed all of their assigned NDR exercises, the research study team will be able to access their completion status via an automated report. Participants who have completed all of their assigned study activities will be emailed a link for them to complete the Post-Intervention Survey 2 on the REDCap survey platform. Participants are expected complete the Post-Intervention Survey 2 within 7 days of completing all of the Assigned NDR Exercises.

Anticipated participant time required to complete Survey 2: 25 minutes

1-Month Post-Intervention Survey 3: Study participants will be emailed a link to Survey 3 which will be hosted on REDCap and is to be completed online. Participants will be sent this survey for completion one-month after completion of Survey 2. Participants are expected to complete the 1-Month Post-Intervention Survey 3 within ± 14 days of being sent the survey link. If a participant misses either of the follow-up surveys (Survey 3 and/or Survey 4), they will continue to be enrolled in the study.

Anticipated participant time required to complete Survey 3: 25 minutes

3-Month Post-Intervention Survey 4: Study participants will be emailed a link to Survey 4 which will be hosted on REDCap and is to be completed online. This is the final study activity. Participants will be sent this survey for completion three-months after completion of Survey 2. Participants are expected to complete the 3-Month Post-Intervention Survey 3 within ± 14 days of being sent the survey link.

Anticipated participant time required to complete Survey 4: 30 minutes

Data collection instruments by time-point listed below:

Data Collection Instrument	Consent (1)	Enrollment (2)	Survey 1 - Baseline (3)	Survey 2 - Post-Intervention (4)	Survey 3 - 1-Month (5)	Survey 4 - 3-Month (6)
e-Consent (survey)	✓					
Post-Consent - Survey 1 Instructions		✓				
Participant Contact Information		✓				
Participant Communication Log		✓				
Screener	✓					
Enrollment Status	✓					
Study Completion Compliance	✓					
Gift Cards - Survey 1		✓				
Gift Cards - Survey 2		✓				
Gift Cards - Survey 3		✓				
Gift Cards - Survey 4	✓					
Positive Affect & Wellbeing (survey)			↓		↓	↓
PROMIS SF - Anxiety (survey)			↓		↓	↓
Caregiver Burden - Zarit (survey)			↓		↓	↓
Neuro-QoL Caregiver SF - TBI-CareQOL Caregiver-Specific Anxiety (survey)			↓		↓	↓
PROMIS SF - Fatigue (survey)			↓		↓	↓
PROMIS SF - Emotional Support (survey)			↓		↓	↓

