PROMIS SF - Satisfaction Roles Activities (survey)			↓		↓	↓
PROMIS SF - General Self-Efficacy (survey)			↓		↓	↓
Sociodemographics (survey)			↓		↓	↓
Acceptability - USE (survey)				↓		
Usability - SUS (survey)				↓		
Dutch Test for Conflict Handling (DUTCH) (survey)			↓	↓	↓	↓
Negotiation Knowledge (survey)			↓	↓	↓	↓
Negotiation Utilization (survey)				↓	↓	↓
PANAS (survey)			↓		↓	↓
IAGO Post-Assessment [Perceived Success] (survey)				↓		

For the purposes of distributing and mailing study compensation, as well as collecting contact information necessary for data collection, the following identifiers will be collected in Aim 1 and Aim 2 of this study:

- Participant name
- Mailing address
- Email address
- Phone number

At the conclusion of the study, once final study analysis is complete, study participants will receive a summary of the findings in layman terms and next steps. In addition, upon request, study participants will receive a copy of this study's primary findings manuscript once it has been published.

8.0 Research with Vulnerable Populations (if children are the ONLY vulnerable population you plan to enroll, do NOT complete this section -- instead fill out Appendix A): N/A

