STATISTICAL ANALYSIS PLAN

Version Date: 3/12/2024

NCT04837937

Aim 2: Utilizing Multiphase Optimization Strategy (MOST), conduct a randomized pilot trial of the NDR intervention that targets better communication between caregivers and health teams, using a 23 full factorial design, to (2a) determine the feasibility of delivering the intervention, and (2b) derive estimates of the effect of 3 intervention components on changes in patient-centered outcomes at post-intervention and follow-up.

Exploratory Aim 3: Explore if intervention components (lectures/exercises) interact to change communication between caregivers and health care teams at post-intervention and follow-up.

Research Design: Randomized Pilot Trial (Aims 2 & 3). Aim 2 will use a 2³ full factorial trial design to test 3 binary components. Individuals will be randomized to 1 of 8 experimental conditions (Table 1). As shown in Table 1, participants can be assigned to intervention ("Yes") or control ("No") conditions for each component. Participants will be blinded to their experimental condition, but everyone will receive "caregiver-patient" negotiation exercise so that no participant gets an inactive placebo.

Unlike the two-arm RCT, the factorial trial compares combinations of conditions to test main effects of and interactions between exercises. For example, to test the main effect of the NDR exercise between caregiver-physician, conditions 1-4 are compared to conditions 5-8 (see **Data Analysis**). In this way, participants are "recycled" across conditions to contain the sample size.

Participants & Recruitment. We will plan to enroll 130 family caregivers in the study.

Procedure & Randomization. Interested individuals will complete a brief screen by telephone to assess potential eligibility. Potentially eligible individuals will be screened and invited to enroll in the intervention and consent using e-Consent. Randomization will be performed using study-ID embedded URL links a-priori to assign participants to an experimental condition with an 8:1 ratio.

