Table 1: Full Factorial Design

Experimental Condition	NDR Exercises by Relationship Conflict Content			
	Caregiver - Patient – Easy [Constant]	Caregiver-Caregiver	Caregiver-Physician	Caregiver - Patient – Difficult
1	Yes	No	No	No
2	Yes	No	No	Yes
3	Yes	No	Yes	No
4	Yes	No	Yes	Yes
5	Yes	Yes	No	No
6	Yes	Yes	No	Yes
7	Yes	Yes	Yes	No
8	Yes	Yes	Yes	Yes

Table 2: Study Components, Time-Points

Intervention		Follow-Up Surveys		
Baseline Survey (T1)	Intervention Completion	Post-NDR Survey (T2)	1 Month (T3)	3 Month (T4)

including themes of spirituality, meaning, mastery, and control, which provided the most important issues facing caregivers. The extensive care needs of individuals with AD are variable, and care typically involves great demands on spouses and other family members.¹¹⁹⁻¹²¹ By examining the wellbeing of the family caregiver as a primary outcome, we will be able to detect how the demands and care needs of their loved ones are affected by the interventions. In addition, among family caregivers of people with AD, there are high rates of anxiety, stress, and depression.^{122,123} Research has shown that poor caregiver mental health was associated with increased patient mortality, even after controlling for sex, age, dementia severity, and patient mental health.¹²⁴ Family caregivers experience anxiety when advocating for their loved ones health care needs.¹²⁵ NDR training may minimize anxiety. Thus, we will measure secondary outcomes of 1.) Anxiety (Patient-Reported Outcomes Measurement Information System (PROMIS) - Anxiety) and Neuro-QoL Caregiver-specific Anxiety¹²⁶ 2.) Caregiver Stress (Caregiver Stress Index), 3.) Caregiver Burden (Zarit Family Caregiver Burden Scale)¹²⁷ 4.) Fatigue (PROMIS)¹²⁸, 5.) Self-Efficacy as measured by PROMIS General Self-Efficacy and Caregiving Self-efficacy scales¹²⁹⁻¹³¹ and 6.) Received Support as measured by PROMIS Emotional/Informational Support, and Social Roles.

Table 3: Process and Patient-Centered Outcome Measures

Constructs	Measurement	Months		
		0	1	3
Patient Centered Outcomes				
Well-Being	(Primary outcome) Neuro-QOL – Positive Affect and Well-Being – Short Form	X	X	X
Anxiety	*PROMIS Ca Adult Item Bank Emotional distress-Anxiety; NEURO-QoL Caregiver Specific Anxiety	X	X	X
Satisfaction with Social Roles	PROMIS Ca Satisfaction with social roles/activities	X	X	X
Caregiver Burden	Zarit Family Caregiver Burden Scale	X	X	X
Fatigue	PROMIS Ca Fatigue	X	X	X

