Self-Efficacy	PROMIS General Self-Efficacy – Short Form, Caregiving Self Efficacy	X	X	X
Received Support	PROMIS Emotional Support – Short Form, PROMIS Informational Support – Short Form, PROMIS Satisfaction with Social Roles/Activities	X	X	X
Intervention Specific Outcomes				
Feasibility	Study Recruitment Rates (count)	X	X	X
	Study Retention Rates (count)	X	X	X
	Acceptability (USE & SUS)	X		
	Completion of NDR Training Exercises	X		
Negotiation Processes/Communication	Dutch Test for Conflict Handling (DUTCH)	X	X	X
	Knowledge of Negotiation Strategies (Survey)	X	X	X
	Utilization of Negotiation Strategies (Survey)		X	X
Program Assessment	Perception of the assigned intervention program, satisfaction, progress. Likert scale. Open-ended questions to obtain qualitative data on subjects' perception.	X	X	X

Qualitative Measures. In addition to the quantitative measures, we will ask qualitative interview questions immediately after the NDR training, and at 1 and 3 months. The open-ended question immediately after the training will ask about how the NDR training was perceived, means to improve, and any areas that were missing. At the 1- and 3-month intervals, the interview will ascertain the perceptions of family caregivers towards the NDR training, experiences with conflict or dispute resolution, and the utility or real-world use of the NDR training. Table 4 provides sample questions. These constitute a preliminary draft set of questions; we will work with our community partners to refine and finalize the items. Our team has extensive experience in health literacy and the development of easy-to-understand interviewer-administered surveys and protocols. Through these in-depth interviews we will explore the attitudes and beliefs of our participants regarding their knowledge, perceptions, and use of the NDR training intervention materials.

Table 4: Sample Questions for Qualitative Interviews

1. Have you experienced any conflicts pertaining to the care of your adult with AD? If so, can you please describe it?
2. Have you used the NDR training? If so, how? Please describe the situation. If not, why?
3. What aspects of the NDR training have been the most valuable? Least valuable? Surprising? Why?
4. How has NDR training affected your ability to handle conflicts?
5. Are there any other aspects of your life where you have used the NDR training? Please describe.

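### Aims 2b and 3 promise effects at post-intervention, but the patient-centered outcomes skip the post-intervention survey, and the communication measures collected there have no stated analysis

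*SAP*

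**What the plan says.** **Aims.** Aim 2b (protocol section 1.0 and the opening of the SAP, same wording) is to "derive estimates of the effect of 3 intervention components on changes in patient-centered outcomes at post-intervention and follow-up". Exploratory Aim 3 asks whether components "interact to change communication between caregivers and health care teams at post-intervention and follow-up".

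**Time points.** SAP Table 2 has four surveys: baseline (T1), "Post-NDR Survey (T2"), 1 month (T3) and 3 months (T4). Protocol section 7.0, Aim 2, describes the second one: "Participants are expected complete the Post-Intervention Survey 2 within 7 days of completing all of the Assigned NDR Exercises". It then separates the later two: "If a participant misses either of the follow-up surveys (Survey 3 and/or Survey 4), they will continue to be enrolled in the study".

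**Collection.** In the protocol's instrument schedule, the row "Positive Affect & Wellbeing (survey") is marked at Surveys 1, 3 and 4, and its Survey 2 cell is empty. The row "Dutch Test for Conflict Handling (DUTCH) (survey") is marked at all four surveys.

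**Analysis.** SAP Table 3 lists outcomes under Months 0, 1 and 3 only. The section on quantitative analyses for Aims 2 and 3 sets the Aim 2b window for the primary outcome as baseline to one month after the intervention. It takes baseline as the reference and models effects as component-by-time interactions. For Aim 3 it names body weight and binge eating as the outcomes, not a communication measure.

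**The concern.** The aims, the collection schedule and the analysis text should agree on when each effect is estimated. Here they do not, and the mismatch runs in two directions.

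- **An aim without data.** Aim 2b claims a post-intervention effect on outcomes that are not asked at the survey bearing that name.
- **Data without an analysis.** Aim 3's post-intervention question could be answered from Survey 2, but the outcome table gives that survey no column of its own and the analysis section gives it no contrast.

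The SAP's Power Calculation section says that the effect sizes will decide which components are kept and will be used to power the next trial. Anyone using an effect size for that purpose needs to know which time point it belongs to. If the plan is silent, the choice for the communication measures would be made after the data are seen.

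**Working it through.** No sample size, power or alpha figure bears on this point. The check sets the two documents side by side.

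**Step 1. Which survey is post-intervention?** Protocol section 7.0 titles Survey 2 the post-intervention survey and groups Surveys 3 and 4 as follow-up. The compensation table in section 13.0 calls Survey 2 immediate post-intervention.

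**Step 2. What is collected when?**

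| Measure | Protocol schedule: surveys marked | SAP Table 3: months marked |
|---|---|---|
| Positive affect and well-being (primary) | 1, 3, 4 | 0, 1, 3 |
| PROMIS anxiety | 1, 3, 4 | 0, 1, 3 |
| Caregiver-specific anxiety | 1, 3, 4 | 0, 1, 3 |
| Zarit burden | 1, 3, 4 | 0, 1, 3 |
| Fatigue | 1, 3, 4 | 0, 1, 3 |
| Emotional support | 1, 3, 4 | 0, 1, 3 |
| Satisfaction with roles | 1, 3, 4 | 0, 1, 3 |
| General self-efficacy | 1, 3, 4 | 0, 1, 3 |
| DUTCH | 1, 2, 3, 4 | 0, 1, 3 |
| Negotiation knowledge | 1, 2, 3, 4 | 0, 1, 3 |
| Negotiation utilization | 2, 3, 4 | 1, 3 |
| USE and SUS | 2 | 0 |
| Exercise completion | not in the schedule (automated report) | 0 |

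The empty Survey 2 cells are unlikely to be a layout accident: in the same schedule USE and SUS are marked at Survey 2 only, and DUTCH at all four.

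**Step 3. Aim 2b.** The first eight rows are the scheduled scales that map to SAP patient-centered outcomes. Number marked at Survey 2: 0 of 8.

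**Step 4. What does Month 0 mean?** For well-being it can only be T1. For USE, SUS and exercise completion it can only be after training. For the program-assessment row it must be T2, because the SAP's Qualitative Measures text places those questions right after training and at 1 and 3 months. So the column holds both kinds of item. DUTCH and knowledge are collected at T1 and at T2, and the table does not show whether their Month 0 mark means T1, T2 or both. Utilization is collected at T2, but its Month 0 cell is blank.

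**Step 5. Is there a T2 contrast in the analysis text?** None is stated for any outcome. The Aim 2b sentence stops at 1 month, and the Aim 3 sentence names outcomes that this trial does not list.

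**Step 6. Scale of the T2 data.** With the protocol's target of 120 completers and every survey returned, DUTCH and knowledge each have 120 × 3 = 360 post-baseline records, of which 120 (one third) are from T2. This is a count of survey waves and measures neither bias nor lost power.

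**The case against.** The strongest reply is that *post-intervention* need not mean Survey 2. The protocol titles Surveys 3 and 4 as 1 and 3 months post-intervention, the SAP's Aim 2b window ends at one month post-intervention, and SAP Table 2 appears to place T2 under the follow-up heading. On that reading Aim 2b has data. Leaving well-being out of Survey 2 also looks deliberate: the Survey Time Points section explains 3 months as allowing enough time to use the training and detect change. Both points stand. They show that the term needs a definition, but they leave the T2 communication data without a stated analysis.

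Four stronger readings are tempting and are not supported:

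- *A T2 value would serve as the baseline and cancel the training effect.* T1 is labelled baseline in both documents, and the models use baseline values as the reference. Nothing directs an analyst to T2.
- *T2 data are excluded from the models.* Table 3 is indexed by month and excludes nothing explicitly, and the mixed models refer generally to multiple assessment times. The T2 contrast is unstated, not ruled out.
- *T2 is needed because daily care stress blurs later readings.* The SAP raises that caveat, under Potential Challenges, about caregiver well-being, which T2 does not measure. It does not raise it about negotiation measures.
- *The primary analysis is compromised.* Its baseline and 1-month data are both scheduled.

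It is also fair to say that this is a pilot, which the SAP states is not powered for hypothesis testing. That limits the consequences, but the pilot's product is a set of effect sizes, each of which needs a time point.

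**Conclusion.** The point holds in a limited form. On the protocol's own survey labels, Aim 2b's post-intervention effect on patient-centered outcomes cannot be estimated, because 0 of 8 mapped scales are collected at Survey 2. That conclusion depends on reading *post-intervention* as Survey 2. The only way round it is to read the term as the 1-month survey, a definition the SAP does not give. Aim 3's post-intervention communication question does have data, but no separate T2 column and no stated contrast.

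The defect lies in what the plan claims and specifies. The documents give no ground for claiming bias in the 1-month analysis of well-being. Correction is worthwhile because it settles what the trial may conclude at each time point, at almost no cost.

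**What to change.** 1. **Aim 2b.** Reword it so that patient-centered outcomes are estimated at 1 and 3 months only, with no immediate post-intervention claim. Reconcile this with the analysis section, whose window stops at 1 month, by naming 1 month as the primary contrast and 3 months as the later one.
2. **SAP Table 3.** Split Month 0 into T1 and T2. Mark DUTCH and knowledge at T1 to T4 and utilization at T2 to T4. Move USE, SUS and exercise completion to T2.
3. **Aim 3 analysis text.** Name DUTCH and knowledge as the outcomes in place of weight and binge eating. State T1 as the reference, T2 minus T1 as the post-intervention contrast, and T3 minus T1 and T4 minus T1 as the follow-up contrasts. Utilization has no T1 value, so it cannot enter as change from baseline.

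The cost is an edit to the aim wording, one table and one paragraph, with no new data collection and no change in sample size. The downside is that Aim 2b's stated scope becomes narrower.

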*Note: The NDR tool will host four negotiation exercises. In order to ensure sufficient feedback for all of the exercises, while also not burdening the research study participants by asking them to complete all four exercises, participants will all review negotiation Exercise 1. The study coordinator will then assign an additional exercise to each participant for two exercises per participant. The exercises differ based on conflict topic and who the negotiation role-play scenario involves. The four negotiation exercises are as follows: Exercise 1: Caregiver vs. Older Adult Patient - Easy [Constant: All participants will view this]; Exercise 2: Caregiver vs. Caregiver; Exercise 3: Caregiver vs. Physician; and Exercise 4: Caregiver vs. Older Adult Patient [Advanced].

(2) Negotiation Learning Materials: Resources & Videos

Next, study participants will be re-directed from IAGO back to the research study website, which hosts negotiation learning materials and resources. Participants will review three documents hosted on the resources page: (1) High Performance

[figure not shown]
Negotiation Strategies checklist, (2) Interests-Rights-Power Negotiation Framework Summary and (3) Negotiation Planning template.

Additionally, study participants will watch five videos hosted on the study website related to the negotiation content and strategies. The videos will cover the interests/right/power negotiation framework and negotiation tactics. Each video is approximately three minutes long; the longest video is about seven minutes. The total time needed to watch all five videos will be approximately 20 minutes. We will ask for feedback about the resources in general with a focus on clarity and perceived utility.

Once all study participants complete Cycle 1, we will share the findings with the team and decide on modifications to the NDR tool based on the feedback/usability testing results. We will make user-driven refinements after each cycle of usability testing. We will repeat this process twice if needed. We anticipate it will take up to 3 months between the first and second cycles of feedback. Once we make changes to the NDR tool, we will repeat this process during Cycle 2 with the same set of study participants and repeat the procedures above, *only if there are sections that were refined based on Cycle 1 feedback*. We will again ask participants to interact with the NDR tool on Zoom and provide both qualitative and quantitative feedback.

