After Cycle 1 and Cycle 2, which will only occur if needed, of usability testing are complete, we will email all study participants a link to the final NDR tool. If Cycle 3 is needed, participants will run through the NDR tool independently and then fill out an online survey hosted on REDCap. This survey will include a modified version of the USE Scale (a measure of usefulness, satisfaction, ease of use, and ease of learning) to measure the participant's final satisfaction with the tool. Additionally, we will ask participants to complete a brief, semi-structured interview over the phone to assess the overall NDR tool's acceptability, satisfaction, and overall impressions. This semi-structured interview will help enhance the quantitative data collected in Cycle 3.

Aim 2: All study timepoints will take place online (REDCap survey) with the exception of the study screener (phone) and e-CONSENT (participant will view online while research study coordinator is on the phone).

Baseline Survey 1: Participants who consent to participate in the study will be sent a link to the REDCap Baseline Survey 1 to their email address. The Research Study Coordinator will confirm that the Baseline Survey 1 link was received while they are still on the call with the participant after the e-Consent to ensure it was sent to the correct email address, was not in a Spam/Junk folder, etc. Participants will have 7 days to submit their completed Baseline Survey 1.

Anticipated participant time required to complete Survey 1: 35 minutes

Study Intervention - Assigned NDR Exercises: Once the completed Baseline Survey 1 is received from the study participant, the Research Study Coordinator will send them a unique study link which includes their embedded randomization assignment (pre-randomized) to their email. The link will give participants access to the study website, www.NegotiAge.com, as well as the negotiation platform where they will access their assigned NDR exercises, IAGO. Participants will have 14 days to complete their assigned exercises.

Anticipated participant time required to complete Study Intervention – Assigned NDR Exercises*: 10-30 minutes

*Participants will be randomized to which/how many negotiation activities they are required to do so we are providing a range of time.

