Data Collection. We will utilize REDCap Surveys software for data entry.¹³² REDCap is a secure, encrypted, Web-based application designed to support data capture for research studies, providing 1) an intuitive interface for validated data

entry; 2) audit trails for tracking data manipulation and export procedures; and 3) automated export procedures for seamless data downloads to common statistical packages. This software allows for straightforward electronic entry of responses and can generate output data files compatible with statistical programs. Drs. [name] and [name] will oversee the database structure and quality assurance activities.

Data Analysis: Power Calculation. The goal of this research is to inform a RCT trial of an optimized intervention. We will achieve that goal by evaluating feasibility and generating effect sizes of each component on changes in outcomes. The effect sizes will inform which components to retain in the optimized intervention and be used to power a subsequent trial. The pilot trial is not powered for hypothesis testing; however, a power calculation was run to determine the effect size this pilot trial will be powered to detect. With 120 subjects total and 40 subjects in each component group, we will be able to detect effect sizes of 0.65 with 80% power using a two-sided t-test at a type I error rate of 5%. For the primary outcome of Neuro-QOL Positive Affect and Well-Being, this equates to a mean difference of 3.9, assuming a standard deviation of 6. Calculations employed Rochon's GEE method, as implemented in SAS GEESIZE v. 3.1 macro implemented by Dahmen.¹³³⁻¹³⁶

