Data Analyses: Aims 2 and 3 Quantitative. Data will be stored on a HIPAA-compliant server with secure access for approved study staff. Analyses will be conducted using SAS 9.4. For **Aim 2a**, we will calculate averages of acceptability ratings, number of exercises completed (retention to treatment), and prescribed strategies documented (compliance). These data will be used to derive expected usage rates for a future trial. For **Aim 2b**, we will assess the effect of each component on changes in Neuro-QOL – Positive Affect and Well-Being across time (baseline-1 month post-intervention), which will be done by comparing combinations of participants across conditions. Analyses will be conducted using intent-to-treat linear mixed effects models, accounting for data collected at multiple assessment time points nested within individual participants. For each component, we will test differences in change in outcomes across time, with baseline values as the reference. Thus, the effects will be modeled as component x time interactions. Cohen's *d* will be calculated by dividing the mixed effects model derived intervention effect estimate by the pooled standard deviation of the outcome. We will also report results disaggregated by sex and test sex as a moderator to evaluate sex differences in outcomes, which will inform the need for any sex-specific approaches in an optimized intervention. For **Aim 3**, exploratory analyses using linear mixed models will be performed to test two-way interactions between components on changes in weight and binge eating (e.g., Component 1 x Component 2 x time). Interaction tests are to determine if a set of components impact the overall effect and thus should be retained together in the optimized intervention.

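### The SAP's worked example labels the caregiver-caregiver comparison in Table 1 as the caregiver-physician main effect

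*SAP*

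**What the plan says.** The SAP's Research Design section describes a 2³ full factorial trial with eight conditions, refers the reader to Table 1 for their content, and gives one example of a main-effect test: "to test the main effect of the NDR exercise between caregiver-physician, conditions 1-4 are compared to conditions 5-8". It then points to Data Analysis.

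Table 1, under the column heading "NDR Exercises by Relationship Conflict Content", lists Yes or No for each exercise in each condition. The columns run: caregiver-patient easy (constant), caregiver-caregiver, caregiver-physician, caregiver-patient difficult.

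The Aim 2b text (Data Analyses: Aims 2 and 3 Quantitative) specifies linear mixed models in which "the effects will be modeled as component x time interactions". It gives no condition numbers and does not say how the component indicators are coded.

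The Power Calculation section states the use of the results: "The effect sizes will inform which components to retain in the optimized intervention". The same estimates are to be used to power the next trial.

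**The concern.** The example and Table 1 sit in the same SAP version and cannot both be right. The split of 1-4 against 5-8 separates the caregiver-caregiver column, not the caregiver-physician column.

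The example is the only sentence in the SAP that names the conditions to be compared for a given main effect. If it guided the coding of the physician indicator, the caregiver-caregiver estimate would appear under the physician label. The choice of components to retain, and the effect size carried into the next trial, would then rest on the wrong exercise. Aim 2 targets communication between caregivers and health teams, so the physician exercise is the component closest to that aim.

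**Working it through.** **Inputs.** Condition coding from SAP Table 1; the stated comparison from SAP Research Design; 130 to be enrolled from SAP Participants & Recruitment; 120 subjects, a detectable difference of 3.9 points and SD 6 from SAP Power Calculation.

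**Step 1: try to reproduce the stated comparison from Table 1.**

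| Component | Yes in conditions | Share Yes in 1-4 | Share Yes in 5-8 | Difference |
|---|---|---|---|---|
| Caregiver-caregiver | 5, 6, 7, 8 | 0/4 | 4/4 | 1 |
| Caregiver-physician | 3, 4, 7, 8 | 2/4 | 2/4 | 0 |
| Caregiver-patient difficult | 2, 4, 6, 8 | 2/4 | 2/4 | 0 |

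Write each condition mean as b0 + b1·(caregiver-caregiver) + b2·(physician) + b3·(patient difficult), with 0/1 indicators. With equal cells, the mean of 5-8 minus the mean of 1-4 is 1·b1 + 0·b2 + 0·b3. The stated comparison does not reproduce the physician effect; it is the caregiver-caregiver effect. If there are interactions, it is still the caregiver-caregiver effect, averaged over the levels of the other two components.

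Taking 5-8 as the physician Yes group, the example disagrees with Table 1 in conditions 3, 4, 5 and 6. Taking 1-4 as Yes, it disagrees in 1, 2, 7 and 8. Either way, four of eight conditions are wrong and the correlation with Table 1's physician column is 0.

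**Step 2: unequal cells.** The physician weight is the share of physician Yes in 5-8 minus the share in 1-4.

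- 130 spread as evenly as possible (two cells of 17, six of 16; all 28 placements): the largest weight is 33/65 − 32/65 = 1/65 = 0.015, and the smallest is −0.015.
- 120 of those 130 completing at random (assumption; 20,000 draws): SD 0.027, 95% range −0.051 to +0.051.
- Simple equal-probability randomization of 120 (assumption; about 60 on each side): SD about √(2 × 0.25/60) = 0.091, or 0.093 by simulation, so a 95% range of about ±0.18.

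Under all three, the weight on caregiver-caregiver stays at 1.

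**Step 3: size of a mislabel.** The error in the reported physician effect is b1 − b2 with equal cells. The SAP's figures agree with each other: 3.9/6 = 0.65 SD.

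| True caregiver-caregiver effect | True physician effect | Reported as physician under the example | Error |
|---|---|---|---|
| 3.9 | 0 | 3.9 | +3.9 |
| 0 | 3.9 | 0 | −3.9 |
| equal | equal | the common value | 0 |

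**Step 4: would the model expose it?** Take a design matrix with an intercept, caregiver-caregiver and patient-difficult from Table 1, and physician from the example. Two columns are identical, so the rank is 3 of 4 and the fit fails visibly. With all three components from Table 1 the rank is 4 of 4. The error stays silent if components are fitted one at a time, or if the caregiver-caregiver and physician labels are swapped. The SAP does not say whether the three components enter one model.

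**Step 5: which text is more likely to be right?** Table 1 has eight distinct rows in standard binary order. Its columns follow the exercise numbering in Protocol Section 7.0 ("Exercise 2: Caregiver vs. Caregiver; Exercise 3: Caregiver vs. Physician"). Both facts favour Table 1. The operative allocation is embedded in the study links, fixed in advance (Protocol Section 7.0; SAP Procedure & Randomization), and the documents do not show it.

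**The case against.** The sentence begins as an example, sits in the design description and defers to Data Analysis, where no wrong contrast appears. Table 1 by itself fixes all three main effects, and Research Design refers to it as the definition of the conditions. The example gives no grouping for the other two components, so a programmer needs Table 1 in any case. For harm to follow, someone would have to ignore the column headed caregiver-physician and then either fit components singly or swap the labels. The 3.9 points is a detectable difference assigned to one exercise, not an expected error. The narrow bounds assume near-equal cells, while the SAP states no blocking and gives an unclear 8:1 ratio.

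Much of this stands. The consequence is conditional, 3.9 points is an illustration, and simple randomization widens the bound to about ±0.18. None of it removes the contradiction. The section to which the example defers does not correct it, the one explicit statement of a contrast carries the wrong label, and the silent routes to error remain open because the SAP does not say how the indicators are coded or whether they are fitted together.

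**Conclusion.** The concern holds. Under Table 1 as printed, conditions 1-4 against 5-8 is the caregiver-caregiver main effect: weight 1 on that component and 0 on the other two with equal cells. With unequal cells the physician weight is at most 0.015 for an even spread of 130, and about ±0.18 (95% range) under simple randomization of 120, so the conclusion does not depend on exact balance.

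The contradiction is certain; its effect on the results is not. If the indicators follow Table 1, the estimates are correctly labelled. If the physician indicator follows the example, the error is the caregiver-caregiver effect minus the physician effect, from zero when they are equal to 3.9 points (0.65 SD) in either direction when one exercise has the SAP's detectable difference and the other has none. Sample size and power are unaffected, because either comparison sets four conditions against four. The text should be corrected before the analysis is run, since component selection depends on these labels.

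**What to change.** First check Table 1 and the example against the allocation embedded in the study links, then reconcile the two. If Table 1 is confirmed, replace the example with the full set of comparisons:

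- caregiver-caregiver: 5, 6, 7, 8 against 1, 2, 3, 4
- caregiver-physician: 3, 4, 7, 8 against 1, 2, 5, 6
- caregiver-patient difficult: 2, 4, 6, 8 against 1, 3, 5, 7

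If the allocation shows that Table 1's columns are mislabelled, correct the table instead. In either case, add a clause to the Aim 2b text saying that the three component indicators in the mixed model are derived from the confirmed Table 1.

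The cost is one corrected sentence (or table), one added clause and one check of the allocation list. Design, sample size and data collection do not change.
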